7.2 Method and Timing of Assessments

Safety will be evaluated using serious adverse events, vital signs, clinical laboratory tests and electrocardiograms. Refer to [Table 1](#) for the frequency and timing of assessments.

Where time-points of different measurements and/or blood samples coincide, the following sequence applies:

1. Vital Signs
2. ECG
3. Safety labs
4. Biomarkers (blood)
5. Pharmacokinetic sample collection

7.2.1 Adverse Event Recording

Adverse events will be recorded from the time the subject signs the informed consent form through trial completion final visit/early termination.

7.2.2 Spontaneously Reported Adverse Events

Spontaneously reported AEs; either volunteered by the subject, prompted by non-directed questioning or reported by an investigator will be documented on the CRF.

7.2.3 12-Lead ECGs

Standard resting 12-lead ECGs will be obtained after subject is resting in the supine position for 10 minutes at the time points listed in [Table 1](#). Additional ECGs may be obtained if clinically indicated.

Overall interpretation and machine read intervals (HR, PR, QRS, QT, and QTc) will be recorded on the ECG eCRF. Clinically significant ECG findings, per the Investigator's clinical judgment, that emerge after treatment will be recorded on the AE CRF.

7.2.4 Safety Laboratory Tests

All safety laboratory analyses will be conducted at local laboratory and have been listed below. Laboratory tests will be obtained as indicated on the Schedule of Events ([Table 1](#)).

Female subjects of childbearing potential will have a urine or serum pregnancy test performed locally at Screening and on Day 28.

Chemistry: Alanine aminotransferase (ALT), aspartate transaminase (AST), total bilirubin, alkaline phosphatase (ALP), total bile acids, sodium, potassium, chloride, bicarbonate, urea, glucose, calcium, uric acid, serum creatinine, creatinine kinase, albumin, total cholesterol, (LDL and HDL), triglycerides, gamma-glutamyl transpeptidase (GGT), and C-reactive Protein (CRP).

Hematology: White cell count with differential (neutrophils, lymphocytes, monocytes, eosinophils, basophils), red blood cell count, hemoglobin, hematocrit, platelet count, mean corpuscular volume, and red cell distribution width.

Urinalysis: Macroanalysis for bilirubin, blood, specific gravity, pH, protein, glucose, ketones, urobilinogen. Dipstick urinalysis is permitted.

Coagulation: PT, INR

7.2.5 Vital Signs

Systolic/diastolic blood pressure, heart rate, respiratory rate, oxygen saturation, and temperature will be measured with specific attention to pulmonary abnormalities. Vital signs will be measured prior any blood collection. Measurements will be taken at the times specified in the Schedule of Events (Table 1) and will be recorded on the appropriate source document and CRF.

7.2.6 Physical Examination

Due to restrictions in patient contact related to COVID-19 infection, a physical examination will only be performed when feasible. The exam includes general appearance, evaluation of head, eyes, ears, nose, throat, neurological exam, weight with specific attention to worsening in liver function as noted by increasing jaundice, ascites (based on International Ascites Club Criteria), or hepatic encephalopathy (based on West Haven Criteria) and presence of infection. The Physical Exams will be taken at the times specified in the Schedule of Events (Table 1) and will be recorded on the appropriate source document and CRF. Any changes from baseline outside the normal range that emerge after treatment will be recorded on the AE CRF.

7.2.7 Biomarkers

Biomarkers will only be assessed when feasible. PPD/CCI

The time window for sample collection can be within 12 hours. Serum samples should be stored at -65°C to -80°C until analysis or according to local laboratory instruction.

The following is a list of planned biomarkers. However, additional non-genetic biomarkers may be included if warranted.

- Subset of cytokines: PPD/CCI

- High-sensitivity C-reactive protein (hsCRP)
- Lactate dehydrogenase (LDH)
- Ferritin and D-dimer
- Soluble urokinase plasminogen activator receptor (suPAR)

The biomarker data at baseline and at each post-dose time point will be plotted and listed for each subject for evaluation of any change from baseline over time. Since the baseline level of each marker may vary from subject to subject, percent change from baseline will be derived at each post-dose time points for each subject.

See Section 7.2 for sequencing when time-points of different measurements and blood sample types coincide.

The nominal sample times will be provided in the CRFs. The actual sample times (times when samples are actually taken) will be recorded alongside the nominal times in the CRF and will be entered at the time of or as soon as possible after sampling.

Blood Volume to be taken during the study:

No more than PPD/CCI of blood will be collected for protocol-related samples collection.

7.3 Adverse Events

7.3.1 Definitions

Adverse Event

An adverse event (AE) is any untoward medical occurrence in a subject or clinical investigation subject administered a pharmaceutical product and which does not necessarily have to have a causal relationship with this treatment. An AE can therefore be any unfavorable and unintended sign or symptom, including clinically significant laboratory values and test results, concomitant illness, accident, or worsening of an existing medical condition.

The following should not be recorded as an AE if noted at screening:

- A pre-planned procedure for an illness included in the subject's medical history, unless the condition for which the procedure was planned has worsened since subject's informed consent. Please observe that complications to pre-planned procedures should be recorded as AEs
- A pre-existing condition found as a result of screening procedures

Any worsening in severity or frequency of a baseline concomitant illness or any new illness diagnosed in the trial period must be regarded as an AE.

Serious Adverse Event

A serious adverse event (SAE) is any adverse event that, at any dose:

- Results in **death**
- **Is life-threatening**
Life-threatening refers to an event in which the subject is at risk of death at the time of the event. It does not include an event that, had it occurred in a more severe form, might have caused death
- Requires inpatient **hospitalization** \geq 24 hours or prolongation of existing hospitalization
Prolongation of hospitalization as determined by the Investigator
- Results in persistent or **significant disability**/incapacity
Disability is defined as a substantial disruption of a person's ability to conduct normal life functions
- Results in the birth of a child with a **congenital anomaly**/birth defect
- **Important medical events** that may not result in death, be life threatening, or require hospitalization may be considered an SAE (when based upon appropriate medical judgment). *These events may jeopardize the subject and may require medical or surgical intervention to prevent one of the outcomes listed above.*

Unexpected Serious Adverse Event

An unexpected serious adverse event (USAE) is any serious adverse event that is independent of the underlying liver disease causality and is not consistent with information in the current Investigator's Brochure, the protocol, and the consent document.

Adverse Reaction

An adverse reaction (AR) is any untoward and unintended response to a test drug that has been considered to have a causal relationship with the treatment.

Suspected Unexpected Serious Adverse Reaction

A suspected unexpected serious adverse reaction (SUSAR) is an adverse reaction that is serious and where the nature or severity of which is not consistent with information in the current Investigator's Brochure.

Abnormal Laboratory Value as an AE

An abnormal laboratory value (i.e. any clinical laboratory abnormality or change that suggests a disease and/or organ toxicity and is of a severity that requires active management [i.e. change of test drug dose, discontinuation of test drug, medical treatment, more frequent follow-up or diagnostic investigation]), will be regarded as an AE. If clinical sequelae have been associated with a laboratory abnormality the diagnosis or medical condition should be reported (e.g. renal failure, hematuria) to replace the laboratory abnormality (e.g. elevated creatinine, urine RBC increased).

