Trial Population: Subjects diagnosed with SARS-CoV-2 infection with acute lung, liver injury or acute kidney injury (AKI)

Inclusion Criteria:

1. Age 18-80 years old and able to provide written informed consent (either from subject or subject's legally acceptable representative)
2. Hospitalized with documented COVID-19 infection diagnosed by standard RT-PCR or equivalent testing other than anti-COVID-19 antibody testing (either upon entry into the hospital, in the hospital, upon admission to the ICU, or in the ICU)
3. Hospitalized with moderate, severe, or early critical COVID-19 illness:
 - a. Mean arterial pressure (MAP) \geq 60 mm Hg, including patients who require no more than one intravenous pressor at the time of enrollment;
 - b. If the subject is on ventilator at the time of Day 1 dosing, the total days on ventilator should be $<$ 5 days (120 hours).
4. Subject meets one (lung only) or two (lung with liver or kidney) of the following criteria at the time of enrollment:
 - a. Acute liver injury irrespective of known, suspected, or unknown hepatic fibrosis or cirrhosis:
 - In subjects without a known history of liver disease and with a documented normal ALT level within past 12 months, acute liver injury will be defined as ALT $>$ 2 ULN and bilirubin $<$ 2.5 mg/dL
 - In subjects with a known history of liver disease and/or a known baseline ALT level within past 12 months, acute liver injury will be defined as ALT $>$ 2x baseline level and bilirubin $<$ 2.5.

- b. AKI:
 - Creatinine increase ≥ 0.3 mg/dL (26.52 μ mol/L) in 48 hours or increase ≥ 1.5 times baseline within the prior 7 days.
- c. Moderate COVID-19 pneumonia defined by the following:
 - Severe bilateral diffuse infiltrates & ground glass opacities involving more than 50% of the lung fieldsOR
 - PaO₂ to FiO₂ ratio 100 to 300.
5. Women of child-bearing potential (defined as women gender assigned at birth) who are not surgically sterile or who are not over the age of 52 and amenorrhoeic for at least 12 months) must utilize appropriate birth control throughout the study duration. Acceptable methods that may be used are abstinence, birth control pills (“The Pill”) or patch, diaphragm, IUD (coil), vaginal ring, condom, surgical sterilization or progestin implant or injection, or sexual activity limited to a sterile (e.g., vasectomized) male partner.

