3.8 CURRENT TRIAL

3.9 Trial Objectives and Primary Endpoints

Primary:

- Evaluate safety in subjects treated with DUR-928 as evidenced by treatment-emergent serious adverse events (TESAEs), including
 1. Respiratory failure events

- 2. Liver failure events
 - 3. Renal failure events
 - 4. Heart failure events
 - 5. Secondary infection (regardless viral or non-viral)
- Evaluate efficacy of DUR-928 in treatment of acute organ failure, especially acute liver or kidney injury, in subjects infected with SARS- CoV-2. The primary efficacy endpoint is the composite of being alive and free of acute organ failure at Day 28. This is specifically defined as being:
 - Alive at Day 28
 - Free of mechanical ventilation at Day 28
 - Free of acute liver failure (i.e., free of the simultaneous presence of: jaundice, coagulopathy, ascites, and hepatic encephalopathy) at Day 28
 - Free of renal replacement therapy at Day 28

Secondary:

- Alive at Days 28 and 60
- Alive, out of ICU, at Day 28
- Alive, out of hospital, at Days 28 and 60

PPD/CCI

[Redacted text block containing multiple lines of blacked-out content]

¶ [REDACTED]

¶ [REDACTED]

¶ [REDACTED]

¶ [REDACTED]

¶ [REDACTED]

¶ [REDACTED]

¶ [REDACTED]

¶ [REDACTED]

¶ [REDACTED]

¶ [REDACTED]

¶ [REDACTED]

¶ [REDACTED]

¶ [REDACTED]

¶ [REDACTED]

¶ [REDACTED]

¶ [REDACTED]

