3.11.1 Inclusion Criteria

To participate in this study, subjects must meet all of the following criteria:

1. Age 18-80 years old and able to provide written informed consent (either from subject or subject's legally acceptable representative)
2. Hospitalized with documented COVID-19 infection diagnosed by standard RT-PCR or equivalent testing other than anti-COVID-19 antibody testing (either upon entry into the hospital, in the hospital, upon admission to the ICU, or in the ICU)
3. Hospitalized with moderate, severe, or early critical COVID-19 illness:
 - c. Mean arterial pressure (MAP) \geq 60 mm Hg, including patients who require no more than one intravenous pressor at the time of enrollment;
 - d. If the subject is on ventilator at the time of Day 1 dosing, the total days on ventilator should be $<$ 5 days ($<$ 120 hours).
4. Subject meets one (lung only) or two (lung with liver or kidney) of the following criteria at the time of enrollment:
 - a. Acute liver injury irrespective of known, suspected, or unknown hepatic fibrosis or cirrhosis:
 - In subjects without a known history of liver disease and/or with a documented normal ALT level within past 12 months, acute liver injury will be defined as ALT $>$ 2x ULN and bilirubin $<$ 2.5.

- In subjects with a known abnormal baseline ALT level within past 12 months, acute liver injury will be defined as ALT >2x baseline level and bilirubin <2.5.
- b. AKI:
- Creatinine increase ≥ 0.3 mg/dL (26.52 $\mu\text{mol/L}$) in 48 hours or increase ≥ 1.5 times baseline within the prior 7 days
- c. Severe COVID-19 pneumonia defined by the following:
- Severe bilateral diffuse infiltrates & ground glass opacities involving more than 50% of the lung fields
- OR
- PaO₂ to FiO₂ ratio 100 to 300.
5. Women of child-bearing potential (defined as women gender assigned at birth) who are not surgically sterile or who are not over the age of 52 and amenorrhoeic for at least 12 months) must utilize appropriate birth control throughout the study duration. Acceptable methods that may be used are abstinence, birth control pills (“The Pill”) or patch, diaphragm, IUD (coil), vaginal ring, condom, surgical sterilization or progestin implant or injection, or sexual activity limited to a sterile (e.g., vasectomized) male partner.
6. Male subjects must agree to use a medically acceptable method of contraception/birth control and refrain from sperm donation throughout the study duration

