 - e. In any subjects with signs and symptoms of fatigue, nausea, vomiting, right upper quadrant pain or tenderness, fever, rash, and/or eosinophilia ($> 5\%$ or $> 500/\mu L$)
2. Worsening of COVID-19 severity
3. SAE events associated with cardiac, kidney, liver, or secondary infection.

The DMC also will be contacted on an as needed basis by the medical monitor to review available data, unblinded by intervention group, providing insights about whether any unexpected SAE (or SUSAR) could be due to study drug rather than the underlying COVID-19 disease and to provide advice regarding study conduct.

In accordance with the Charter, the DMC review of unblinded data will occur promptly to address situations listed in Section 11.5, for example,

- PPD/CCI [REDACTED]
- more than 2 subjects have an AE grade 3 or above on the CTCAE scale that is determined to be possibly or probably attributable to study drug as per the medical monitor;
- more than 3 deaths, and the overall percentage of study patients with deaths within 60 days exceeds 10%.

Based on data review, DMC could recommend termination of the trial, pausing of randomization, discontinuation of treatment, or continuation of the trial.

Refer to Section 11.5.

The following parameters will be recorded daily for the safety evaluation:

- Serious adverse events

- Standard 12-lead ECG
- Safety Laboratory Tests (clinical chemistry, hematology, coagulation, and urinalysis)
- Vital Signs
- Physical examination (when feasible)

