7.3.2 Adverse Event Reporting

All events that meet the definition of an AE and occur in the period from when the subject has signed the informed consent form (ICF) through trial completion (final visit), or early termination, must be recorded on the adverse event CRF. All SAEs will be recorded on the appropriate CRF and on the Serious Adverse Event Report Form from the time written informed consent has been obtained through trial completion (final visit), or early termination.

At each contact between the investigative site and the subject (visit or phone), after the subject has had an opportunity to spontaneously mention any problems, the Investigator should inquire about the occurrence of AEs. The following are examples of open-ended questions that may be used to obtain this information:

“How are you feeling?”

“Have you had any medical problems since your last visit/assessment?”

“Have you taken any new medicines, other than those given to you in this study, since your last visit/assessment?”

All AEs and SAEs will be documented in source records at each assessment time or when otherwise volunteered by the subject and recorded on the appropriate CRF. Information to be collected includes the nature, date and time of onset, severity, duration, relationship to test drug, and outcome of the event. Even if the Investigator assesses the AE as not reasonably attributable to the test drug, its occurrence must be recorded in the source documents and reported on the CRF along with the assessment of association.

The Investigator will treat the subject as medically required, and this may extend beyond the duration of the trial. The Investigator will record treatment and medications required to treat AEs on the appropriate CRF(s). All SAEs, and any possibly/probably related severe AEs will be followed until resolution. Resolution of an AE is defined as that point in time when no further changes in the event are expected, that is, the point at which a subject experiencing such an AE is appropriately treated and stabilized even though they may continue to experience lingering sequelae that may never resolve.

DURECT’s designee will evaluate all AEs with respect to seriousness, causality and expectedness in accordance with Directive 2001/20/EC (3) and FDA Guidelines. The expectedness of an AE will be determined according to the current version of the Investigators Brochure.

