11.5 Data Monitoring Committee (DMC)

An independent, external DMC that includes a hepatologist, a nephrologist and an ICU specialist will convene prior to study start, once the PPD/CCI [REDACTED] enrolled and their PK data available, once PPD/CCI [REDACTED] have been treated and followed for PPD/CCI [REDACTED] to monitor the study for safety events including SAEs, death, premature discontinuation of treatment for SAEs, or any treatment-emergent laboratory abnormalities.

DMC will evaluate (based on an unblinded review of safety data) if there is:

1. PK data and safety review of the PPD/CCI [REDACTED];

2. a >20% of subjects in the DUR-928 group than in the placebo group with treatment-emergent, treatment-related serious adverse event(s) of a specific type;
3. more than 3 deaths, and the overall percentage of study patients with deaths within 60 days exceeds 10%.
4. more than 2 subjects have an AE grade 3 or above on the CTCAE scale that is determined to be possibly or probably attributable to study drug as per the medical monitor.

The DMC also will be contacted on an as needed basis by the medical monitor to review available data, unblinded by intervention group, providing additional insights about whether any unexpected SAE (or SUSAR) to an individual subject could be due to study drug rather than the underlying COVID-19 disease and to provide advice regarding study conduct. The PI and medical monitor, based on the nature and severity of the event(s) under the Individual Subject Stopping Rule as listed below, will determine if such event(s) warrant the early termination of the study therapy in the best interest of the subject. The DMC may also provide recommendations as needed.

Individual Subject Stopping Rule:

1. Appearance of DILI:
 - a) If baseline measurements (BLM) were <2x ULN, discontinue if ALT or AST increases to >5x BLM;
 - b) If BLM \geq 2x ULN but <5x ULN, discontinue if ALT or AST increases to >3x BLM;
 - c) If BLM \geq 5x ULN, discontinue if ALT or AST increases to >2x BLM;
 - d) Discontinue if ALT or AST increase > 2x BLM AND the increase is accompanied by a concomitant increase in TBL to >2x BLM OR the INR concomitantly increases by >0.2 in absence of COVID-19 coagulopathy;
 - e) In any subjects with signs and symptoms of fatigue, nausea, vomiting, right upper quadrant pain or tenderness, fever, rash, and/or eosinophilia (> 5% or > 500/ μ L)
2. Worsening of COVID-19 severity

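### The unexpected-SAE definition in 7.3.1 excludes events by liver disease, not COVID-19, and conflicts with the plan's other expectedness rules; the effect is limited to the timing of as-needed DMC referral

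*Combined protocol and SAP*

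**What the plan says.** Section 7.3.1 sets two conditions for an unexpected SAE, joined by an and. The event must be "any serious adverse event that is independent of the underlying liver disease causality", and it must be one that "is not consistent with information in the current Investigator's Brochure, the protocol, and the consent document".

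Other parts of the protocol use different tests:

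- **SUSAR definition, also in 7.3.1.** The event must be a reaction considered causally related to the test drug. Its nature or severity is compared with the Investigator's Brochure only. There is no liver clause.
- **Section 7.3.2.** "The expectedness of an AE will be determined according to the current version of the Investigators Brochure". There is no disease clause, and neither the protocol nor the consent document is mentioned.
- **Section 7.1.** The medical monitor contacts the DMC as needed to review unblinded data, "providing insights about whether any unexpected SAE (or SUSAR) could be due to study drug rather than the underlying COVID-19 disease". Section 11.5 asks the same question, whether the event "could be due to study drug rather than the underlying COVID-19 disease".

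On the population, inclusion criterion 4 in 3.11.1 reads "Subject meets one (lung only) or two (lung with liver or kidney) of the following criteria at the time of enrollment". The synopsis has the same rule. On the safety objective, 3.9 lists "Liver failure events" among the primary treatment-emergent SAEs.

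**The concern.** A definition of unexpectedness that refers to an underlying disease should name the disease all subjects share. Here it names one that many subjects need not have. The sections that use the idea of an unexpected SAE name COVID-19 instead, and the section that sets the expectedness standard names no disease.

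This matters because an unexpected SAE is one of the two categories, with the SUSAR, that 7.1 and 11.5 give for as-needed contact with the unblinded DMC. In a subject with lung and liver injury, a serious liver event can readily be put down to the liver condition. The first condition in 7.3.1 then removes it from the unexpected category, even if nothing like it appears in the Investigator's Brochure. Attribution is hardest for such events, and the unblinded comparison between arms is most informative there.

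**Working it through.** No arithmetic applies. The plan gives no figure on this point, and the claim rests on no rate, sample size or error level. The check is to take the tests listed above and apply them to typical events.

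**Case 1: a liver SAE attributed to liver disease, not judged drug-related, and absent from the Investigator's Brochure.**
- Unexpected-SAE definition in 7.3.1: fails the first condition, so it is not unexpected.
- Section 7.3.2: unexpected.
- SUSAR: no, because causality is required.
- As-needed DMC referral: outside it under the 7.3.1 definition, inside it under 7.3.2. The same event gets opposite answers.

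**Case 2: a liver SAE judged drug-related and absent from the Investigator's Brochure.**
- It can meet the SUSAR definition, which has no liver clause and shares the as-needed route. The clause does not block it.

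**Case 3: a respiratory SAE caused by COVID-19 in a lung-only subject.**
- It passes the liver condition, since there is no liver disease to depend on.
- It must still meet the second condition. Respiratory failure is named in the protocol's own safety objective (3.9), so it may be called consistent with the protocol and hence not unexpected.

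**Case 4: the Case 1 event is a liver failure, and only the liver clause is deleted.**
- The second condition still refers to the protocol and consent document. The protocol lists liver failure in 3.9, so the event could still be called consistent with the protocol and not unexpected.
- Section 7.3.2, using the Investigator's Brochure alone, would still say the opposite. Deleting the clause is therefore necessary but not sufficient.

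**What still captures the Case 1 event.**
- Section 7.3.3: every SAE is reported within 24 hours, regardless of causality. This report does not go to the DMC.
- Sections 7.1 and 11.5: liver SAEs fall under the individual subject rule and are evaluated by the investigator and medical monitor. DMC input is optional there.
- Section 11.5: scheduled unblinded DMC review covers SAEs and treatment-emergent laboratory abnormalities whatever their label.
- Section 11.5: if the event is fatal, it counts toward the criterion on deaths. The criteria on treatment-related SAEs of a specific type and on attributable AEs of grade 3 or above would not count it, because both depend on attribution to study drug.

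For a non-fatal event of this kind, scheduled review is thus the main assured route to the DMC. Parts of the meeting schedule in 11.5 are blacked out, so the possible delay cannot be calculated.

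**The case against.** The strongest reply is that the clause has little practical force, for four reasons.

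First, the DMC sees all SAEs unblinded at its planned meetings, and SUSARs reach it without any liver test. This stands. A reader might infer that liver SAEs are kept from DMC review, but the documents do not support that. What can be lost is prompt referral of one class of event.

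Second, only events attributed to liver disease fail the clause; a liver SAE judged to be caused by the drug does not depend on that disease. This also stands, and it narrows the point to events whose attribution may be mistaken. It does not remove the point, because the SUSAR route and two of the section 11.5 criteria depend on the same attribution.

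Third, liver disease is not foreign to the trial. Acute liver injury is in the title, section 3.11 describes the population by liver or kidney injury, and the DMC includes a hepatologist. That is fair, but even 3.11 admits subjects with kidney injury and no liver disease, and criterion 4 admits lung-only subjects. Liver disease cannot serve as the underlying disease for everyone.

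Fourth, the DMC text does not use the defined abbreviation, its contact is as needed, and the charter, which is not among the documents, may settle the matter. This is possible. Within the protocol, however, 7.3.1 is the only definition of an unexpected SAE, and nothing says that 7.3.2 overrides it.

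A reader might also infer that COVID-19 events are automatically swept into the unexpected category. Case 3 shows why that does not follow. Sections 7.1 and 11.5 in any case ask the DMC to separate drug effect from COVID-19, so some such referrals are intended.

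**Conclusion.** The definition is wrong as written and should be corrected. It names a disease that not all subjects have, and it conflicts with the SUSAR definition and 7.3.2 on the expectedness standard and with 7.1 and 11.5 on the underlying disease.

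The effect is small and specific. A liver SAE attributed to liver disease and not judged drug-related can miss the as-needed referral of unexpected SAEs and wait for scheduled review. The primary efficacy analysis, sample size and SAE reporting duty are untouched.

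The number of affected events cannot be determined. A reader might multiply the planned 60 DUR-928 subjects (80 × 3/4) by a guessed share with liver injury. That would count subjects, not events, and the documents give no share, event rate or attribution rate.

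The conclusion assumes that unexpected SAE in 7.1 and 11.5 carries the 7.3.1 meaning, and that the charter does not set a different rule.

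**What to change.** Make two changes to the one sentence in 7.3.1:

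1. Delete the condition that the event be independent of underlying liver disease.
2. Replace the reference to three documents with the current Investigator's Brochure, so that the sentence matches the SUSAR definition and 7.3.2.

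Add no substitute disease clause. Whether an event is due to the drug or to COVID-19 is a causality question, and the DMC text in 7.1 and 11.5 already asks it. Check that the charter uses the same definition.

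The cost is a one-sentence protocol amendment with the usual ethics approval. The downside is that a few more SAEs may be referred to the DMC.
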